2.1 Background

Myelodysplastic syndromes (MDS) are malignant clonal disorders characterized by ineffective hematopoiesis, bone marrow dysplasia, peripheral cytopenias including thrombocytopenia, and a propensity to transform into acute myeloid leukemia (AML).^{1,2} Classically, MDS is associated with apoptosis and excessive proliferation, resulting in a paradoxical combination of a hyper-cellular marrow and peripheral cytopenias.³ The incidence of MDS in the United States is rising, with approximately 20,000 to 30,000 new cases of MDS diagnosed annually, and a median age at diagnosis of 70 years.³⁻⁶

The therapeutic options for MDS remain limited. A small percentage of patients are candidates for curative therapies such as allogeneic stem cell transplant. For the vast majority of patients the lack of acceptable donors, advanced age, and/or serious comorbid medical conditions and organ dysfunction prevent access to this option. For essentially the same reasons, AML-like chemotherapy regimens represent an unacceptable benefit/risk ratio for many of these patients. In fact, the standard of care in MDS has generally been accepted as supportive in nature.

Over the past decade, clinical use of the hypomethylating agents (HMA) azacitidine and decitabine have been shown to improve patient quality of life, decrease transfusion requirements, and improve outcome parameters in MDS patients, and are now the standard of care for MDS patients requiring therapy. However, not all patients respond to HMAs, and unfortunately most patients initially responding to HMAs will ultimately progress on therapy. Current evidence suggests ORRs of 28-48% and CR rates of 6-34% in all patients treated with HMAs, with a median length of response in HMA-responders of only 8 to 10 months.^{6,7} Myelosuppression, including severe thrombocytopenia, is commonly seen in HMA-treated patients, and is the most frequent cause of dose reduction, delay and discontinuation of HMA agents in up to 80% of patients.⁸ Currently there are no thrombopoietic agents indicated for use in MDS.

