Interim results from the first clinical trial (NCT02488565) are available in abstract form from the EHA 2013 meeting. In this trial, n=17 patients have been started on 50mg of eltrombopag and dose-escalated every 2 weeks up to 300mg daily. One patient developed reversible grade III LFT abnormalities, and 4 patients developed thrombocytosis requiring eltrombopag cessation. Activity was seen in 76% (4 CR, 3 marrow CR, 3 HI-P, 1 HI-E, 2 with >50% bone marrow blast reduction) and platelet improvement was seen in 8/15 (53%) patients with baseline platelets <100K. One patient had an improvement in platelet count during the lead-in 2-week 50mg eltrombopag phase. Treatment with the combination of eltrombopag and azacitidine at doses up to 300mg were well-tolerated, with encouraging response and AE events.

Interim results from the second trial (NCT01481220) are also available from the EHA meeting. This pilot study explores eltrombopag with increasing doses of eltrombopag (from 50mg to 300mg in a 3+3 dose-escalation fashion) in conjunction with standard azacitidine dosing, and reports on n=11 patients. Reported SAEs were one case of fatal pneumonia with E. coli septicemia, erysipelas (occurring twice in n=1 patient), and bronchitis (n=1). One patient developed DLT with an extremity DVT, elevated liver enzymes and progressive disease at the n=300mg dose. The combination of eltrombopag with azacitidine was summarized as feasible and well-tolerated.

Additionally, in a Phase II study of 25 patients with refractory aplastic anemia²¹, eltrombopag monotherapy was administered to all patients at a dose of 50mg, with dose escalation to a maximum dose of 150mg daily possible. All but one patient in this study received the maximum dose of 150mg per day, and 11 of 25 patients obtained a platelet response. Serious adverse events in this cohort included abdominal pain and orthostatic hypotension in a patient with diabetic gastroparesis, a severe rash that was temporally related to the initiation of cephalosporin, severe gingival bleeding associated with thrombocytopenia, and episodes of fever with neutropenia. One patient acquired

Hepatitis B virus infection during the study and eltrombopag was discontinued. Diagnosis of a cataract in one patient at week 9, during examination for a “floater”, prompted the discontinuation of eltrombopag, although the patient met hematologic response criteria. The cataract could not be confirmed on subsequent examinations.

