- Make every reasonable attempt to have subjects return to clinic within 24-72 hours for repeat liver chemistries and liver event follow-up assessments (see below)
- Monitor subjects weekly until liver chemistries (ALT, AST, alkaline phosphatase, bilirubin) resolve, stabilize or return to within baseline values.

For all Criteria 1-5, make every attempt to carry out the liver event follow-up assessments described below as clinically appropriate:

- Viral hepatitis serology (Hepatitis A IgM antibody; Hepatitis B surface antigen and Hepatitis B core antibody (IgM); Hepatitis C RNA; Cytomegalovirus IgM antibody; Epstein-Barr viral capsid antigen IgM antibody; Hepatitis E IgM antibody if subject resides outside the USA or Canada or has travelled outside the USA or Canada in the past 3 months).
- Serum creatine phosphokinase (CPK) and lactate dehydrogenase (LDH).

- Obtain complete blood count with differential to assess eosinophilia
- Record use of concomitant medications, acetaminophen, herbal remedies, other over the counter medications, or putative hepatotoxins.
- Record alcohol use
- Liver imaging (ultrasound, magnetic resonance, or computerized tomography) to evaluate liver disease.

4.7.1.2. Dose Adjustments Related to Platelet Count:

The starting dose for all study patients (with the exception of East Asians, see 4.7.1.3) will be 200mg orally daily. East Asians will start at 100mg orally daily. The eltrombopag dose can be increased by 100mg (to maximum of 300mg daily) after 2 weeks if the untransfused platelet count has not increased to $> 100 \times 10^9/L$ and the patient has not experienced any grade ≥ 3 study drug related toxicity. Laboratory work including a CBC with differential and blood chemistries including ALT, AST and bilirubin must be evaluated bi-weekly for 4 weeks after any change in eltrombopag dosing.

Eltrombopag will be held if platelet counts exceed $400 \times 10^9/L$, and will be resumed the next scheduled day that platelet counts have decreased to $\leq 100 \times 10^9/L$. Dose should be reduced to the next lower dose level, if appropriate.

Dose reductions or delays different than the dose described above are acceptable after discussion with the sponsor and the PI, and will require documentation of the rationale for such action.

4.7.1.3. Dose Adjustments for Subjects of East Asian Ancestry:

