6.2. Study Endpoints

6.2.1. Primary Efficacy Endpoint: The overall response rate (CR + PR + HI) based on the IWG-2006 criteria. Responses must last at least 4 weeks.

Complete Remission:

- Bone marrow: $\leq 5\%$ myeloblasts with normal maturation of all cell lines
- Persistent dysplasia will be noted
- Peripheral blood
 - o Hemoglobin $\geq 11\text{g/dL}$
 - o Platelets $\geq 100 \times 10^9/\text{L}$
 - o Neutrophils $\geq 1.0 \times 10^9/\text{L}$
 - o Blasts 0%

Partial Remission:

- All CR criteria if abnormal before treatment except:
 - o Bone marrow blasts decreased by $\geq 50\%$ over pretreatment but still $> 5\%$

Stable Disease:

- Failure to achieve at least PR, but no evidence of progression for >8 weeks

Failure:

- Death during treatment or disease progression characterized by worsening of cytopenias or significant increase in percentage of bone marrow blasts

Hematologic Improvement (HI) Response Criteria*: responses must last at least 8 weeks

- **Erythroid response** (if pretreatment hemoglobin $< 11\text{g/dL}$)
 - o Hemoglobin increase by $\geq 1.5\text{g/dL}$
 - o Relevant reduction of units of RBC transfusions by an absolute number of at least 4 RBC transfusions/8 wk compared with the pretreatment transfusion number in the previous 8 wks. Only RBC transfusions given

for a Hgb of ≤ 9.0 g/dL pretreatment will count in the RBC transfusion response evaluation

- **Platelet response** (if pretreatment platelets $< 100 \times 10^9/L$)
 - o Absolute increase of $\geq 30 \times 10^9/L$ for patients starting with $> 20 \times 10^9/L$ platelets
 - o Increase from $< 20 \times 10^9/L$ to $> 20 \times 10^9/L$ and by at least 100%
- **Neutrophil response** (if pretreatment $< 1.0 \times 10^9/L$)
 - o At least 100% increase and an absolute increase of $> 0.5 \times 10^9/L$

*Pretreatment counts averages of at least 2 measurements (not influenced by transfusions) for at least one week

Progression or relapse after HI‡:

- At least 1 of the following:
 - o At least 50% decrement from maximum response levels in granulocytes or platelets
 - o Reduction in hemoglobin by ≥ 1.5 g/dL
 - o Transfusion dependence
- ‡In the absence of another explanation, such as acute infection, repeated courses of chemotherapy (modification), gastrointestinal bleeding, hemolysis, and so forth. It is recommended that the 2 kinds of erythroid and platelet responses be reported overall as well as by the individual response pattern.

Relapse after CR or PR:

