- At least 1 of the following
 - o Return to pretreatment bone marrow blast percentage
 - o Decrement of $\geq 50\%$ from maximum remission/response levels in granulocytes or platelets
 - o Reduction in hemoglobin concentration by ≥ 1.5 g/dL or transfusion dependence

Cytogenetic Response:

- Complete: Disappearance of the known chromosomal abnormality without appearance of new abnormalities
- Partial: At least 50% reduction of the chromosomal abnormality in 20 metaphases

Disease Progression:

For patients with:

- Less than 5% blasts: $\geq 50\%$ increase in blasts to $> 5\%$ blasts
- 5-10% blasts: $\geq 50\%$ increase to $> 10\%$ blasts
- 10-20% blasts: $\geq 50\%$ increase to $> 20\%$ blasts
- 20-30% blasts: $\geq 50\%$ increase to $> 30\%$ blasts

Any of the following:

- At least 50% decrement from maximum remission/response in granulocytes or platelets
- Reduction in hemoglobin by ≥ 2 g/dL
- Transfusion dependence

Survival Endpoints:

- Overall: death from any cause
- Event free: failure or death from any cause
- PFS: disease progression or death from MDS
- DFS: time to relapse
- Cause specific death: death related to MDS

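### A platelet fall during the protocol's own eltrombopag hold can be scored as relapse or disease progression, because the alternative-explanation footnote covers only relapse after HI

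*Combined protocol and SAP*

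**What the plan says.** - **Dosing (Section 4.7.1.2).** Eltrombopag is held once platelets exceed 400 ×10⁹/L, "and will be resumed the next scheduled day that platelet counts have decreased to" 100 ×10⁹/L or below. The same section adds: "Dose reductions or delays different than the dose described above are acceptable after discussion with the sponsor and the PI".
- **Scoring (Section 6.2.1).** Three definitions use a fall of 50% or more from the maximum in platelets or granulocytes: *Progression or relapse after HI*, *Relapse after CR or PR*, and *Disease Progression*. The last reads "At least 50% decrement from maximum remission/response in granulocytes or platelets".
- **Footnote (Section 6.2.1).** Only the HI definition carries the qualifier "In the absence of another explanation, such as acute infection, repeated courses of chemotherapy (modification), gastrointestinal bleeding", which goes on to hemolysis and an open-ended remainder.
- **Endpoints built on these definitions.** In Section 6.2.1 a PFS event is disease progression or death from MDS, DFS is time to relapse, and event-free survival counts failure or any death. Section 8.4.2 names PFS as a secondary endpoint, estimates it by Kaplan-Meier, and applies a two-sided log-rank test between groups.
- **Primary endpoint.** ORR is CR + PR + HI. Responses must last 4 weeks, and HI must last 8 weeks.
- **HMA effect (Section 2.1).** "Myelosuppression, including severe thrombocytopenia, is commonly seen in HMA-treated patients".

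**The concern.** The dosing section keeps the drug on hold through a fall that the response section treats as loss of disease control. Two of the three definitions have no way to set that fall aside. The third has one, but it does not settle the matter. The Disease Progression item refers to any remission or response, so a fall excused under the HI definition can still be progression, and no text says which definition takes precedence.

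Time-to-event results could then contain events created by adherence to the protocol. In Arm B the same gap applies to HMA-cycle nadirs in patients who have responded. Repeated chemotherapy courses are a named explanation under HI but not under the other two definitions. Arm A has no HMA nadirs, so this part falls on one side of the log-rank comparison.

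The plan recognises the general problem elsewhere. Section 8.4.2 sets aside hemoglobin and platelet values within 3 days of a transfusion, and excludes patients on other growth factors from the HI analysis for the periods in Section 4.5.3. It has no matching rule for its own drug hold.

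**Working it through.** **1. Size of the fall.** Inputs are the hold and resume thresholds of Section 4.7.1.2. For a peak M above 400 and a resumption count of at most 100, the fall is at least 1 − 100/M.

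| Peak M | Fall on reaching 100 | Count at which the 50% item is met |
|---|---|---|
| 401 | 75.1% | 200.5 |
| 500 | 80.0% | 250 |
| 800 | 87.5% | 400 |

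The 50% line is crossed at M/2, above 200, while the rule still keeps the drug on hold. The documents state no figure of their own for this fall.

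**2. How that fall is scored.**

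| Definition (Section 6.2.1) | 50% item met? | Footnote available? | Feeds |
|---|---|---|---|
| Progression or relapse after HI | Yes | Yes, open-ended | Relapse |
| Relapse after CR or PR | Yes | No | DFS |
| Disease Progression | Yes | No | PFS, possibly event-free survival |

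Event-free survival is only possible because Failure requires death, or progression characterized by worsening cytopenias or a significant blast increase. Every entrant has platelets below 100 (Section 3.1), so a count of 100 is not below baseline. Section 2.3.3 does warn that stopping eltrombopag may leave platelets lower than before therapy.

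**3. Does the fall break a response?** For a baseline b above 20, HI-P needs a count of at least b + 30. At a count of 100 that holds when b ≤ 70 and fails for baselines 71 to 99. CR needs platelets of at least 100. PR inherits that requirement, because platelets were abnormal at entry. Resumption at 100 or below therefore meets the CR/PR platelet criterion only at exactly 100. ORR changes only if this happens before the 4 or 8 weeks are complete and no other HI lineage qualifies.

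**4. Frequency.** The only related figure is in Section 2.2: "4 patients developed thrombocytosis requiring eltrombopag cessation", out of 17 (4/17 = 23.5%; exact 95% CI 6.8% to 49.9%). Applied to 23 patients it gives 0.235 × 23 = 5.4. The design targets imply 0.18 × 23 = 4.1 responders of any kind in Arm A and 0.25 × 23 = 5.75 in Arm B. The rate would put more Arm A patients above 400 than are expected to respond at all. It also comes from a combination trial, with no platelet count given for cessation. It is not a usable estimate.

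**5. Sensitivity of ORR, by assumption only.** For each two-stage design, P(success) = Σ P(X₁ = x) · P(X₂ ≥ r − x) over x ≥ 1, with r = 3 (Arm A, 15 then 23 patients) and r = 4 (Arm B, 12 then 23). This reproduces the plan: power 80.2% and 85.4% (stated 80% and 85%), and early termination under the null 46.3% and 54.0%, as stated. If a share f of true responders lost that status, the response rate becomes p₁(1 − f):

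| f (assumed) | Arm A power | Arm B power |
|---|---|---|
| 0 | 80.2% | 85.4% |
| 10% | 73.5% | 78.4% |
| 30% | 55.9% | 58.0% |
| 50% | 33.6% | 31.5% |

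The documents do not give f, and by step 3 it may be close to zero.

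**The case against.** A reader might infer that the strongest platelet responders are counted as failures in the primary endpoint. The documents do not support that:

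- No text withdraws a response that has already met its minimum duration.
- A platelet-only responder is an HI responder, and that relapse definition carries an open-ended footnote into which a documented hold plausibly fits.
- HI-P survives a fall to 100 for baselines up to 70.
- Failure needs more than a percentage fall from peak.

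Nor does the rule force the fall. It makes resumption conditional on it, and Section 4.7.1.2 accepts other reductions or delays after discussion. Under Section 4.6, progression ends treatment only if it is clinically significant. All of this stands, and it limits the point to relapse and progression scoring.

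A reader might also infer that every HMA nadir in Arm B becomes a progression event. The item measures the fall from a maximum remission or response, so it most naturally applies to responders. PFS is missing from the secondary lists in Sections 1.2 and 6.2.3, and the arms are not randomized (Section 5.2), so a between-arm PFS contrast is already confounded. That lowers the weight of the comparison. It does not make the recorded events correct.

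Flexibility over delays alters dosing, not scoring. The two unqualified definitions remain unqualified.

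**Conclusion.** The conflict between Sections 4.7.1.2 and 6.2.1 is real and follows from the text alone. A responder held above 400 and resumed at or below 100 has fallen more than 75%, and two definitions score a 50% fall without exception. PFS and DFS, and possibly event-free survival, can record events caused by the dosing section or, in Arm B responders, by HMA nadirs. This rests on reading the definitions literally and on the footnote mark applying only to the HI heading, where it is printed.

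The number of affected patients cannot be estimated from the documents. The effect on ORR is conditional on an interrupted minimum duration, and no loss of power is established. The passages should be reconciled before responses are adjudicated, because case-by-case decisions afterwards would be open to bias.

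**What to change.** In Section 6.2.1, extend the existing footnote to *Relapse after CR or PR* and *Disease Progression*. Name two explanations: counts taken during a protocol-mandated eltrombopag hold, and HMA-cycle nadir counts that recover by the next evaluable assessment. State when the hold window closes and which maximum applies afterwards: with a peak above 400, half the peak exceeds 200, so any later count of 200 or less still meets the 50% item.

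Leave the 4-week and 8-week requirements for ORR unchanged. Counting interrupted responses toward ORR would loosen the primary endpoint against a fixed 5% null. Report any response interrupted only by a mandated hold in a sensitivity analysis.

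The dosing rule is not touched and the 23 patients per arm do not change. The work is wording in Section 6.2.1 and a line in Section 8.4.2, using blood counts and dosing records already collected. The downside is that a true relapse beginning during a hold or nadir may be dated a few weeks later.

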6.2.3. Secondary Efficacy Endpoints

The key secondary endpoints for this study are:

- The incidence of transformation to AML by FAB during treatment period and follow-up
- The incidence and severity of bone marrow fibrosis during treatment period and follow-up
- Proportion of patients achieving a platelet response during treatment; and proportion of patients achieving a durable platelet response.
 - o Platelet IWG-2006: A complete response is defined as a platelet count $> 100 \times 10^9/L$; and a major response defined as an increase of platelet count by higher than $30 \times 10^9/L$.
 - o Durable platelet count: in which a hematologic improvement in platelets (HI-P) defined as either an increase $\geq 30 \times 10^9/L$ from patients with a baseline platelet count $\geq 20 \times 10^9/L$, or an increase from $< 20 \times 10^9/L$ to $\geq 20 \times 10^9/L$ and by at least 100%, present for ≥ 8 weeks.

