8.4.2. Analysis of Key Study Endpoints

The primary endpoint is overall response rate (ORR). The ORR in each arm will be evaluated along with the exact 95% confidence interval. Given the limited sample size, no formal comparison will be made between these two arms in terms of ORR.

Secondary endpoints include platelet response, durable platelet response, transformation to AML, incidence of bone marrow fibrosis, and time-to-event outcomes such as progression-free survival (PFS) and overall survival (OS). The probabilities of PFS and OS will be estimated using the method of Kaplan and Meier. The incidence rates of other binary secondary endpoints will be estimated, along with the exact 95% confidence intervals. Subjects that discontinue the study prior to having achieved a clinical response will be considered to have not had an event.

Patients receiving growth factors other than eltrombopag (erythropoietin, GM-CSF or G-CSF) will not be considered in the HI analysis for the time periods specified in Section 4.5.3 Supportive Care Guidelines. Hemoglobin levels and platelet counts collected from patients that have received a transfusion within the last 3 days will not be considered in the analysis.

Survival or times to failure and time to progression functions will be estimated using the Kaplan-Meier method. The two-sided log-rank test will be used to assess the differences of time to events between groups.

The total number of dose administrations, the average dose (mg), and the cumulative dose administered will be summarized by eltrombopag treatment group.

Blood chemistry and complete blood counts will be summarized by treatment group at each time point.

Additional exploratory analyses of the key study endpoints will be performed as deemed appropriate.

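### PFS counts only deaths attributed to MDS, with no rule for other deaths, and its progression criteria leave baseline transfusion dependence and some AML transformations unsettled

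*Combined protocol and SAP*

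**What the plan says.** The survival list at the end of section 6.2.1 gives "PFS: disease progression or death from MDS". Its neighbors are "Overall: death from any cause" and "Event free: failure or death from any cause", and death related to MDS is a further, separate endpoint.

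Disease progression in the same section has two parts. The first is a set of blast bands by baseline value, the highest being "20-30% blasts: $\geq 50\%$ increase to $> 30\%$ blasts". The second, headed "Any of the following", lists a fall of at least 50% in granulocytes or platelets from best response, a hemoglobin fall of at least 2 g/dL, and "transfusion dependence". No connector says whether the two parts are alternatives or must both be met.

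Section 6.2.3 has a separate secondary endpoint: "The incidence of transformation to AML by FAB during treatment period and follow-up".

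PFS is named as a secondary endpoint only in section 8.4.2, which says: "The probabilities of PFS and OS will be estimated using the method of Kaplan and Meier". The same section plans a two-sided log-rank test for times to event between groups. It does not say how a death from another cause is handled in PFS.

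**The concern.** PFS normally treats death as an event because a patient who has died cannot progress later. Under this definition a death attributed to infection, bleeding or treatment is not an event, and with Kaplan-Meier and no other rule it becomes a censoring. The result is neither the chance of being alive without progression nor a cumulative incidence. Attribution is a judgment, no blinding is described, and the patient and physician choose the arm (sections 5.2 and 8.1). Arm B continues a drug class that section 2.1 links to frequent myelosuppression, so deaths attributed to treatment could be censored unequally by arm.

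Two smaller problems concern what counts as progression:

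- Transfusion dependence is a state, while its neighbors in the list describe change. Section 3.2 does not exclude dependent patients.
- Section 3.1 (item 2) admits patients with 20-30% blasts. For them the relative-rise requirement can leave a transformation to AML outside the blast criterion.

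At stake is the meaning of a reported PFS curve, not the trial's primary decision.

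**Working it through.** The plan states no rate, event count or power for PFS, so there is no figure to reproduce.

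**1. Deaths not attributed to MDS.** Recoding some events as censored can only raise a Kaplan-Meier curve or leave it unchanged, so the direction is certain. The size needs assumptions.

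- M, median survival: 4 or 5.6 months, cited in section 2.1 for progression after decitabine and after azacitidine. These are survival figures, used here only to set a death hazard.
- k, progression hazard divided by death hazard: 0.5 to 2 (assumed).
- f, share of deaths not due to MDS: 10-30% (assumed).
- Constant, independent hazards, with the death hazard ln 2 / M applying before progression (assumed).

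Six-month PFS with all deaths counted is 2^(−6(1+k)/M). With MDS deaths only it is 2^(−6(1+k−f)/M).

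| M (months) | k | f | All deaths | MDS deaths only | Difference (points) |
|---|---|---|---|---|---|
| 4 | 2 | 0.1 | 4.4% | 4.9% | 0.5 |
| 4 | 1 | 0.2 | 12.5% | 15.4% | 2.9 |
| 5.6 | 1 | 0.2 | 22.6% | 26.3% | 3.6 |
| 4 | 0.5 | 0.3 | 21.0% | 28.7% | 7.7 |
| 5.6 | 0.5 | 0.3 | 32.8% | 41.0% | 8.2 |

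Differences are taken before rounding. The first and last rows are the extremes of the range. In the third row, median PFS is 5.6/2 = 2.8 months with all deaths and 5.6/1.8 = 3.1 months with MDS deaths only.

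**2. Blast criterion against AML by FAB.** Section 6.2.3 gives no cut-off. Section 3.1 treats 20-30% blasts as MDS by FAB, which implies AML above 30%. For an entry value b above 20% and up to 30%, the blast criterion needs at least 1.5 × b, so values above 30% and below 1.5 × b are AML by FAB but miss it:

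- b = 22%: above 30%, below 33%
- b = 25%: above 30%, below 37.5%
- b = 29%: above 30%, below 43.5%

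A change from 25% to 32% is a relative rise of 7/25 = 28%, so it misses. At b = 20%, 1.5 × 20% = 30%, so for entry values of 20% or less any value above 30% is already a rise of more than 50% and there is no gap.

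**3. Transfusion dependence.** The erythroid improvement rule in section 6.2.1 compares transfusions with the previous 8 weeks. The progression item has no baseline period, no unit count and no statement of which blood product it covers. Table 5.3 marks transfusion assessment at screening and next on Day 1 of Cycle 2. If the two progression lists are alternatives and the item is read literally, a patient dependent at entry with unchanged disease meets progression at that first on-treatment assessment. The documents give no baseline share. If 10%, 30% or 50% were dependent (assumption), that would be 2.3, 6.9 or 11.5 of 23 patients in an arm.

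**The case against.** Overall and event-free survival count every death and cause-specific death is listed separately, so no death is lost to the trial. Section 6.2.1 presents its criteria as based on IWG-2006, which cannot be checked from these documents. A cause-restricted endpoint can also be legitimate. All of this stands, and it means the definition should not simply be called wrong. It does not repair PFS, because a cause-restricted endpoint needs an attribution rule and competing-risk handling, and the plan has neither.

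A reader might infer that patients dependent at entry progress on day 1. The documents do not support that. Table 5.3 has no transfusion assessment on Cycle 1 Day 1, the missing connector leaves the logic open, and the failure definition in section 6.2.1 describes progression as worsening cytopenias or a significant blast increase. Unchanged dependence is not worsening. For the same reason it is only arguable that failure and event-free survival carry the same problem.

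A reader might also infer that AML transformations in general fall outside PFS. The gap is confined to patients entering with more than 20% blasts who meet no other progression item, and transformation is reported as its own endpoint in any case.

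Finally, PFS is unpowered, is missing from the secondary lists in sections 1.2 and 6.2.3, and plays no part in the stopping or success rules of sections 8.2 and 8.3. That limits the consequence.

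**Conclusion.** The concern holds in a limited form. Following the plan as written censors deaths not attributed to MDS and biases PFS upward relative to PFS with all deaths counted. The direction does not depend on assumptions. The size, about 0.5 to 8 percentage points at 6 months, rests on the assumed hazards and shares, because the documents supply neither a progression rate nor causes of death.

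The transfusion item is an ambiguity that pulls the other way if read literally. The AML gap is arithmetically certain but narrow. The number of patients affected by either cannot be derived, so the net error in a reported curve cannot be stated, and a claim that PFS is invalid would go too far. The definition should be settled before PFS is analyzed. The response-rate and toxicity decisions are untouched.

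**What to change.** Confine the change to the PFS analysis definition:

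- Define PFS as time to disease progression, AML transformation by FAB (with the blast cut-off stated), or death from any cause.
- Count transfusion dependence only if it was not present at baseline. Define dependence and the baseline period from the transfusion data collected.
- State whether the blast list and the list that follows it are alternatives or must both be met.
- Keep cause-specific death as the separate endpoint already listed.

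Disease progression is also a reason to end treatment in sections 4.6 and 5.6. Those sections should be reconciled with the endpoint definition; no clinical rule is proposed here.

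The cost is mainly wording. The endpoints already planned require deaths and marrow blasts to be recorded. Section 4.5.4 captures platelet transfusions from screening, which section 5.1 places within 4 weeks of first dose, and only the red-cell rule in section 6.2.1 looks back 8 weeks. A longer platelet look-back may therefore need an added case report form field. PFS will look slightly shorter than under the present definition.
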